- 5. Pregnancies complicated by oligohydramnios
- 6. Fetuses with an estimated fetal weight >4500 gm by recent ultrasound or Leopold's exam on admission
- 7. Patients with class 3 obesity (BMI >40)

- 8. Fetuses with a persistent category 2 or 3 fetal heart tracing at labor induction admission
- 9. Vaginal bleeding at the time of randomization
- 10. Any indication for scheduled cesarean delivery
- 11. Hypersensitivity to oxytocin
- 12. Uterine contractions \geq 5 in10 minutes that is sustained for at least 30 minutes
- 13. Hypersensitivity to prostaglandins

Interventions:

- 1. Active group: Mifepristone 200 mg po + Transcervical (Cook) Balloon
- 2. Standard group: Misoprostol 50 mcg po+ Transcervical (Cook) Balloon

Medications:

Mifepristone 200mg po Misoprostol 50 mcg po

Analysis: Intent to Treat

Outcome Measures:

Primary outcomes:

• Generation of preliminary data comparing obstetric and neonatal outcomes among patients randomized to misoprostol 50 mcg versus mifepristone 200 mg

Obstetric outcomes:

- Number of uterine contractions with and without fetal heart rate decelerations during the time the foley is in place
- Rate of uterine tachysystole (≥ 5 contractions in 10 minutes that is sustained for at least 30 minutes) or hypertonus (a single contraction lasting more than 2 minutes) during labor
- Time to delivery
- Time to complete cervical dilation
- Total time on the Labor and Delivery unit
- Rate of cesarean delivery (CD)
- Rate of failed induction of labor per ACOG guidelines
- Composite of serious maternal morbidity based on CDC severe maternal morbidity and mortality (including acute myocardial infarction, aneurysm, acute renal failure, adult respiratory distress syndrome, amniotic fluid embolism, cardiac arrest/ventricular fibrillation, conversion of cardiac rhythm, disseminated intravascular coagulation, eclampsia, heart failure/arrest during surgery or procedure, puerperal cerebrovascular disorders, pulmonary edema/acute heart failure, severe anesthesia complications, sepsis, shock, sickle cell disease with crisis, air and thrombotic embolism, blood products transfusion, hysterectomy, temporary tracheostomy, ventilation)

• Neonatal outcomes:

- Comparison of neonatal cord gases (arterial pH) and neonatal APGAR scores at 1 and 5 minutes

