2.3.5 Assessment of potential risks

No studies indicate that intrapartum exposure to misoprostol (or other prostaglandin cervical ripening agents) has any long-term adverse health consequences to the fetus in the absence of fetal distress, nor is there a plausible biologic basis for such a concern. Although misoprostol currently is approved by the U.S. Food and Drug Administration (FDA) for the prevention of peptic ulcers, the FDA in 2002 approved a new label on the use of misoprostol during pregnancy for cervical ripening and for the induction of labor. This labeling does not contain claims regarding the efficacy or safety of misoprostol, nor does it stipulate doses or dose intervals.¹

According to the FDA, the major adverse effect of the obstetrical use of misoprostol is hyperstimulation of the uterus which may progress to uterine tetany. There is an increase in uterine rupture (requiring surgical repair, hysterectomy, and/or salpingo-oophorectomy) among patients with a known history of a previous uterine surgery.

There may be an increased risk of uterine tachysystole, meconium passage, meconium staining of amniotic fluid, and Cesarean delivery due to uterine hyperstimulation with the use of higher doses of misoprostol. In this study, the standard dose of 50 mcg and 100 mcg as the second dose if indicated will be used. It is established that oral misoprostol reduces risk for cesarean section rate and has a low incidence of uterine hyperstimulation.⁵ The risk of uterine rupture increases with advancing gestational ages and with prior uterine surgery, including cesarean birth and these patients are excluded from this study.

The following have been reported as adverse events in subjects receiving misoprostol: Gastrointestinal: In subjects receiving misoprostol 400 or 800 mcg daily in clinical trials, the most frequent gastrointestinal adverse events were diarrhea and abdominal pain. The incidence of diarrhea at 800 mcg in controlled trials in patients on NSAIDs ranged from 14-40% and in all studies (over 5,000 patients) averaged 13%. Abdominal pain occurred in 13-20% of patients in NSAID trials and about 7% in all studies, but there was no consistent difference from placebo. However, patients will not receive doses greater than 100 micrograms, minimizing the risk for gastrointestinal side effects.

Due to potential risks of misoprostol, the same safety guidelines as stated in 2.3.2 will remain in this study group.

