5.2 Inclusion Criteria

Nulliparous patients aged 18 to 45 years, with singleton live pregnancies of gestational age 37 weeks 0 days – 42 weeks 0 days, with a planned labor induction, not in labor, with intact membranes with no contraindication for vaginal delivery, misoprostol or mifepristone, and a Bishop score <6 with transcervical balloon in place <3 hours prior to the time of randomization, without prior cervical preparation.

For patients who meet the above inclusion criteria 1-10 and who those who decline randomization will be offered enrollment for chart review only.

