5.3 Exclusion Criteria

If the basic screening criteria are met, the next step is to review the exclusion criteria. Those without exclusions should be approached for study participation.

Assess the following exclusions:

- 1. Significant cardiac, renal, or hepatic maternal comorbidities, severe gestational hypertension or preeclampsia with severe features
- 2. Pregnancies complicated by major fetal anomalies
- 3. Patients with a uterine scar

- 4. Pregnancies complicated by fetal growth restriction (estimated fetal weight <10%)
- 5. Pregnancies complicated by oligohydramnios

6. Fetuses with an estimated fetal weight >4500 gm by recent ultrasound or Leopold's exam on admission

- 7. Patients with class 3 obesity (BMI >40)
- 8. Fetuses with a persistent category 2 or 3 fetal heart tracing at labor induction admission
- 9. Vaginal bleeding at the time of randomization
- 10. Any indication for scheduled CD
- 11. Hypersensitivity to oxytocin
- 12. Uterine contractions \geq 3 in10 minutes
- 13. Hypersensitivity to prostaglandins

Patients who meet inclusion criteria and do not have exclusion criteria may be approached for the informed consent process.

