6. RANDOMIZATION

Randomization will occur at the time of labor induction admission.

Randomization may occur upon confirmation that all exclusion/inclusion criteria are satisfied, after verification of participant consent and HIPAA authorization, and a transcervical balloon is placed by the OB provider. Of particular importance, careful consideration will be given to the patient's history and fetal status to determine final eligibility. Study staff will also verify participant contact information and obtain a Release of Information.

The MFM Research team will review the following before randomization:

- Complete review of all exclusion and inclusion criteria
- Informed consent obtained
- Fetal status and cervical exam to confirm eligibility
- Verification by OB provider that transcervical balloon is in place

Pharmacy randomization:

- The LPCH pharmacy will randomize the study medication and dispense to the Labor and Delivery medication dispense system, Pyxis.
- The L&D nurse caring for the participant will provide the medication and instructions

The LPCH pharmacy will attain records of randomization.

Both groups, will undergo continuous external fetal monitoring and tocometry throughout the entirety of labor induction per standard of care.

[figure not shown]
The categories of patients randomized:

Patients consenting to the study will be randomized in 1:1 blocks to two treatment groups

Group 1: Patients randomized to the mifepristone group will receive mifepristone 200 mg po treatment.

Group 2: Patients randomized to the misoprostol group will receive misoprostol 50 mcg po treatment.

Study Design

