pulse measurements will be recorded every 15 minutes for the first hour of the induction process and then hourly during the first 4 hours of the induction process. If 2 vital sign abnormalities are noted during this period, the OB provider will be notified, and the standard of care work up will be initiated. (See section 2.3.2) Abnormal vital signs include Heart rate > 110 beats per minute or <50 beats per minute, systolic blood pressure (mm Hg) > 160 or < 45 or diastolic blood pressure > 110 or < 85 or MAP <65 mm Hg. Patients will assessed for the presence of known potential side effects from mifepristone or misoprostol by patient interview on postpartum day one. All patients will undergo continuous electronic fetal heart rate monitoring and tocometry until the time of delivery.

Cervical exams will be performed per standard of care by OB providers and recorded. The primary outcome is time to complete cervical dilation. Once the patient achieves complete cervical dilation, time spent in the second stage of labor will be at the discretion of the provider.

Placentas will be sent out to Pathology after delivery if deemed indicated for both groups by the provider. Both groups will have their placentas analyzed if there are clinical indications for the test.

Time and mode of delivery will be recorded into the REDCap database.

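### Exclusion 12 carries two different contraction thresholds, and Section 6.2's lower blood-pressure limits count ordinary diastolic readings as abnormal

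*Combined protocol and SAP*

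**What the plan says.** **Exclusion 12.** The synopsis excludes patients with "Uterine contractions \geq 5 in10 minutes that is sustained for at least 30 minutes". Section 5.3, under the same item number, excludes "Uterine contractions \geq 3 in10 minutes" and gives no duration. Section 5.2 requires patients "with a planned labor induction, not in labor, with intact membranes", without a contraction count. Section 6 lists "Complete review of all exclusion and inclusion criteria" among the checks before randomization. Section 5.1 has the numbers screened, eligible and approached entered in REDCap, and recruitment feasibility is a stated outcome (Section 3.1).

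**Blood pressure.** Section 6.2 treats as abnormal a heart rate above 110 or below 50, and also "systolic blood pressure (mm Hg) > 160 or < 45 or diastolic blood pressure > 110 or < 85 or MAP <65 mm Hg". The consequence is stated just before: "If 2 vital sign abnormalities are noted during this period, the OB provider will be notified", and a work-up begins. On timing, mean arterial pressure and "pulse measurements will be recorded every 15 minutes for the first hour of the induction process and then hourly during the first 4 hours". The same part of 6.2 sends the reader to Section 2.3.2. The list there covers temperature, heart rate, MAP below 65 and respiratory rate, and has no systolic or diastolic limit. Section 7.2 repeats the two-sign rule and again refers to 2.3.2. For the misoprostol arm, Section 2.3.5 says that "the same safety guidelines as stated in 2.3.2 will remain in this study group".

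**The concern.** Both items are rules that staff must apply, and neither can be applied as printed.

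For exclusion 12, the two versions disagree about the same patient. Eligibility then depends on which page the screener has open, and so does the eligible count that serves the feasibility aim. Contraction count is also the first-listed obstetric outcome (Section 3.1) and the basis of the detectable difference in Section 4.4. The entry threshold therefore helps define the population whose average and variability the pilot is meant to estimate.

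For blood pressure, a systolic floor of 45 beside a diastolic floor of 85 is not credible. The only diastolic values left as normal are 85 to 110. If an ordinary diastolic uses up one of the two signs, the two-sign rule becomes close to a one-sign rule, and it disagrees with the list in 2.3.2 that it points to.

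**Working it through.** The plan gives no figure to reproduce here. The check is a comparison of text plus simple arithmetic.

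**1. Exclusion 12, for a patient who meets every other criterion**

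| Contractions | Synopsis | Section 5.3 |
|---|---|---|
| 0–2 per 10 min | eligible | eligible |
| 3–4 per 10 min | eligible | excluded |
| 5 or more per 10 min, under 30 min | eligible | excluded |
| 5 or more per 10 min, 30 min or longer | excluded | excluded |

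The versions disagree on the two middle rows. The not-in-labor criterion may already remove some of these patients, but with no count attached it does not decide which threshold applies. Neither version can be set aside as an obvious slip: the synopsis value matches the tachysystole definition in Section 3.1, and the Section 5.3 value is a stricter limit.

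Recruitment forecast (Section 12.2): 800 − 200 = 600 eligible; 600 × 0.5 × 0.5 = 150 willing per year; the target of 30 is 30/150 = 20% of that. The section does not say which version its roughly 200 exclusions reflect, so neither the size nor the direction of any change in the 600 can be stated.

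**2. Blood-pressure limits**

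MAP is taken as (systolic + 2 × diastolic)/3, with diastolic no higher than systolic, so MAP lies between the two.

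- Diastolic of 85 or more gives MAP of at least 85. The diastolic floor therefore sits at least 20 mm Hg above the MAP floor of 65 in the same sentence.
- Systolic below 45 gives MAP below 45, already flagged by MAP below 65. The systolic floor never adds a detection.
- Swapped floors are coherent: 85/45 gives (85 + 90)/3 = 58.3, already under 65.

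Signs counted, with heart rate normal unless shown and each limit counted separately:

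| Reading | MAP | 6.2 as printed | Floors swapped | 2.3.2 list |
|---|---|---|---|---|
| 110/70 | 83.3 | 1 (diastolic) | 0 | 0 |
| 120/80 | 93.3 | 1 (diastolic) | 0 | 0 |
| 120/80, heart rate 112 | 93.3 | 2, triggers | 1 | 1 |
| 90/50 | 63.3 | 2 (diastolic, MAP) | 1 (MAP) | 1 (MAP) |
| 80/50 | 60.0 | 2 (diastolic, MAP) | 2 (systolic, MAP) | 1 (MAP) |

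The protocol does not say whether two limits breached by one reading, or one limit breached at two times, count as two signs.

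**Exposure.** Readings at 15, 30, 45 and 60 minutes and at 2, 3 and 4 hours make 7 per participant, or 8 with one at time 0. Over 30 participants that is 7 × 30 = 210 to 8 × 30 = 240 scheduled readings.

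**Illustration only.** The documents give no distribution of diastolic pressure. If it were normal with mean 65 to 80 and SD 8 to 12 (assumed), the share below 85 would run from Φ((85 − 80)/12) = 66% to Φ((85 − 65)/8) = 99%. The share below 45 would be at most Φ((45 − 65)/12) = 4.8%.

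**The case against.** The strongest reply on blood pressure is that staff already have a workable list. Section 2.3.2 states the two-sign rule with coherent limits, Section 7.2 relies on it, and 6.2 cross-refers to it. A single low diastolic starts nothing, and what a trigger brings is a call to the provider of a continuously monitored inpatient and a routine work-up. This stands as to size. It does not cure 6.2, which prints its own limits and so contradicts the list it cites.

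On exclusion 12, the reply is that Section 5.3 is the working instruction for screeners and the synopsis only a summary, and that the patients in dispute must still satisfy every other criterion. The second part stands: the group may be small. The first does not settle the matter, because no rule of precedence is stated.

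It is also fair to say that these are two unrelated drafting errors. They share an amendment but not a mechanism.

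Several stronger readings are tempting and are not supported:

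- *Hypotension would be missed.* No: MAP below 65 remains in 6.2.
- *The systolic and diastolic limits contradict each other.* Not formally: they are alternatives, so they are implausible together rather than contradictory.
- *Nearly every participant would trigger a work-up.* That would require low diastolics at different times to count as two signs, which the text does not say.
- *Section 2.3.5 carries the 45 and 85 limits into the misoprostol arm.* It refers only to 2.3.2, which has no such limits. The limits apply to both arms because 6.2 itself covers both study groups.
- *The arm comparison is biased or recruitment is at risk.* Eligibility is settled before randomization, no outcome depends on the blood-pressure limits, and the target is 20% of the annual forecast.

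**Conclusion.** Both errors are in the current text and should be corrected. Exclusion 12 is the weightier, because it affects who is randomized and the eligible count reported for feasibility. The share of patients between the two thresholds is not given, so no number can be attached.

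The blood-pressure error is smaller. It makes an ordinary diastolic count as one of two signs, and its effect is limited to false triggers over 210 to 240 scheduled readings; their number cannot be derived. That the floors were transposed is a probable explanation, not something the documents confirm. The arithmetic rests on the usual MAP formula, but the two bounds need only that MAP lies between diastolic and systolic.

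**What to change.** - **Exclusion 12.** The investigators choose one threshold, with its duration, and use identical text in the synopsis, Section 5.3 and the screening form. The documents do not show which value was intended, so the choice is theirs.
- **Section 6.2.** Align it with 2.3.2 by deleting the floors of systolic 45 and diastolic 85 and relying on MAP below 65. Alternatively, if the investigators confirm the transposition, state systolic <85 and diastolic <45 and put the same limits in 2.3.2. Swapping the numbers in 6.2 alone would leave the two lists in conflict.
- While this is open, one sentence should say whether several limits breached by one reading count as one sign or two. A reading of 90/50 counts as two signs in 6.2 as printed if limits are counted separately, but as one under either correction.

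The cost is one text amendment, sent to the IRB as Section 1.5.1 requires, and an update of the screening form. No new data, staff or procedures are needed.

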6.3. Standard Dose of Medications

The FDA has approved mifepristone in a regimen with misoprostol, for the medical termination of intrauterine pregnancy through 70 days gestation. Historically mifepristone 600 mg followed by a prostaglandin were used, however, preferred dosing of mifepristone 200 mg is the current FDA approved dose due to its equal efficacy and safety as compared to 600 mg.^{26,27}

Mifepristone 200 mg in adjunct to misoprostol is used off-label for management of pregnancy loss before 20 weeks and second trimester abortion, including induction of labor and dilation and evacuation. Mifepristone used with misoprostol reduces time to delivery and leads to fewer adverse effects when compared to misoprostol alone.^{7,8}

Mifepristone 200 mg dosing received FDA approval in 2016 and is used as the standard dose in conjunction with misoprostol. Mifepristone 200 mg dose was used as the standard dose among studies of inducing labor at term.^{11,12} However, one study compared mifepristone 50 mg, 100 mg, 200 mg, 400 mg, and 600 mg and found no difference in maternal or neonatal outcomes among dosing.¹³

According to ACOG, one quarter of an unscored misoprostol 100-mcg tablet (ie, approximately 25 mcg) of misoprostol should be considered as the initial dose for cervical ripening and labor induction. However, this is based on a vaginal route. The standard of care at LPCH is 50 mcg orally, based on previous literature that suggests stepwise oral misoprostol (50 mg followed by 100 mg) appears to be as effective as vaginal misoprostol (25 mg) for cervical ripening with a low incidence of hyperstimulation, no increase in side effects, a high rate of patient satisfaction, and is associated with a lower cesarean section rate.⁵

Frequency of dosing varies between every 3-6 hours. At LPCH standard of care is every 4 hours. Repeat doses of misoprostol 50-100 mcg orally will be given if indicated starting 4 hours after first dose.

7. POST RANDOMIZATION

7.1 Post Randomization Patient Satisfaction Survey

All patients will complete a numerical rating scale patient satisfaction survey after balloon removal and on postpartum day one to evaluate medication side effects and overall satisfaction associated with treatment.

7.2 Management of patient's intolerance to study intervention

Most common adverse reactions (>15%) to mifepristone include nausea, weakness, fever/chills, vomiting, headache, diarrhea, and dizziness.

If the patient experiences side effects, the standard of care medications will be used for the patients:

For nausea and vomiting the patient will be offered Zofran 4 milligrams IV or po every 6 hours as needed, Compazine 10 milligrams IV or po every 6 hours as needed, Reglan 10 milligrams IV or po every 6 hours as needed.

For headache the patient will be offered Tylenol 1 gram po every 8 hours as needed. For diarrhea the patient will be offered Lomotil 5 milligrams every 6 hours as needed. For dizziness and weakness, a comprehensive workup will be established to ensure the etiology is neither infectious or neurological.

As stated in 2.3.2, if the patient experiences 2 vital signs that are outside of normal parameters, the standard of care work up will be initiated.

If the patient experiences a fever in labor, per standard of care, antibiotics are started, and an infectious workup is initiated. If the patient has a fever with abnormal vital signs per CMQCC guidelines (see 2.3.2), assessment for infection is initiated per standard of care.

7.8 Study Drug, Dispensing

Stanford's investigational pharmacy will dispense either mifepristone or to LPCH pharmacy. LPCH pharmacy will dispense/administer study drug to research participant's nurse via the Pyxis. The nurse will dispense the medication to the participant.

7.9 Biospecimens

Placentas will be sent out to Pathology after delivery if deemed indicated for both groups by the provider. Both groups will have their placentas analyzed if there are clinical indications for the

test. Assessment will be performed with the standard of care for all LPCH delivering participants.

8. POST-DELIVERY

Outcome Data Collection and Chart Review Delivery Outcomes will be ascertained on an ongoing basis until discharge.

Study personnel will abstract the hospital charts and complete information for REDCap entry:

- Labor and Delivery Data
- Neonatal Outcome Data
- Placental Pathology (if obtained)
- NICU admission form (if indicated)
- Adverse Event
- Study Intervention Discontinuation and Participation discontinuation/withdrawal

9. PROCEDURES FOR INACTIVE/ LOST/ REFUSED PARTICIPANTS AND MISSED VISITS

9.1 Overview

Staff will use a systematic approach in attempting to recover reluctant participants, i.e., those who have either expressed interest in dropping out of the study or appear to be likely to drop-out with any aspect of the study.

The goals to avoid drop-out and accomplish drop-out recovery include the following:

1. to ensure that participants are not pushed to the point that they refuse to participate further 2. to continue to engage participants through some form of contact (e.g., phone, e-mail) and allow an opportunity to determine participants' concerns and problem-solve for solutions to concerns and barriers to participation,

3. to foster some form of continued participation

The general approach to drop-out recovery will involve contact by the study coordinator in an attempt to:

- 1. identify barriers to participation
- 2. problem-solve for solutions to overcome identified barriers
- 3. apply motivational enhancement methods

In situations where a participant's behavior suggests that they **do not** wish to participate, the participant can be removed from the study.

9.2 Definition of Participant Status.

For purposes of the study, we define the following terms related to trial participation status:

• Active status – active if medication therapy is managed according to the study algorithm. The participant continues labor induction per study protocol, which is the standard of care at LPCH.

• Inactive status – participant consents to chart review for study purposes, but does not consent to randomization.

• Lost status –lost-to-follow-up if the participant does not arrive for planned labor induction and cannot be contacted by any ordinary means (e.g., home phone, cell phone, mail, email, fax, etc.), clinic staff does not know the participant's whereabouts, and alternative contacts either do not know where the participant is or cannot be contacted themselves.

• Withdrawn/Refused status –participant is considered to be withdrawn if they have withdrawn consent to participate in the study and refuses further contact for any reason or if the participant consented and no longer meets study eligibility criteria at any point in the study.

